2.1 Background

Nil by mouth (NBM) has been the standard of care for cardiac catheterization since its inception, because of the associated vomiting that was common with the first generation of radio contrast materials that were almost toxic and use of general anaesthesia. Induction of anaesthesia depresses the cough and swallow reflex thus increasing the risk of aspiration, this is also true for deep sedation.

Today, the cardiac catheterization procedure is done under local anaesthesia with anxiolytic sedatives often used peri-procedurally to achieve minimal sedation whereby verbal contact is maintained. Both the royal college of anaesthetists and the royal college of emergency medicine state that fasting is not required for minimal or conscious sedation but does recommend fasting for general anaesthesia.^{1,2} There is only 1% risk of needing emergency surgery for percutaneous coronary interventions (PCIs). The risk of developing pulmonary aspiration following emergency coronary artery bypass grafting (CABG) surgery or emergency direct current conversion (DC) in patients without pre-procedural fasting is in the order of 0.001%.³

There was no evidence that the volume or pH of participants' gastric contents differ significantly between fasting and non-fasting population as shown by Brady et al.⁴ In addition, the overall

incidence of nausea and vomiting was reported to be 1% before elective cerebral angiography in a study carried out by Kwon et al⁵ with no significant difference between fasting and non-fasting group.

Hamid et al⁶ recently conducted a retrospective analysis of registry data for 1916 percutaneous coronary intervention (PCI) patients over a 3 years period. None of the patients were kept nil by mouth (NBM) pre-procedure and no patients required immediate endotracheal intubation nor did any develop aspiration pneumonia intra or post procedurally. They concluded in their observational study that patients undergoing PCI do not need to be fasted prior to their procedures.

The American Society of Anaesthesia guidelines discuss this extensively and have concluded that there is no strong relation between fasting, gastric volume, or risk of aspiration. In any case, the patients at highest risk for nausea and vomiting are those who present with ST-elevation myocardial infarction (STEMI), who are not fasting anyway and the need for emergency intubation/CABG remains rare in these patients.

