2.2 Study Objectives

- To show that allowing patients to eat freely up to the point of elective coronary angiography/angioplasty is not associated with any increased risk of nausea, vomiting, abdominal pain, emergency intubation or aspiration pneumonia compared to patients kept nil by mouth.
- To show improved patient satisfaction when allowed to eat up to the point of elective coronary angiography/angioplasty compared to patients kept nil by mouth.

We aim to provide evidence from a prospective study to help the development of guidelines that can be implemented nationally and internationally regarding pre procedural care of cardiac patients.

3 Study Design

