3.3 Primary Study Endpoints

Primary endpoint is a composite of nausea, vomiting, abdominal pain, emergency intubation and aspiration

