4.5 Withdrawal of Subjects

If any patient chooses to withdraw from the study, they will revert to the standard hospital procedure. However, they will still be included in the final analysis as intention to treat and any drop out or cross over will be documented.

5 Prior and Concomitant Therapy

All previous medication and treatments should continue.

6 Clinical Procedure

As standard practice, operators will be allowed to use any techniques they commonly use throughout their practice (choice of access, balloon and stent type).

7 Statistical Plan

Given that the occurrence of pulmonary aspiration was so low in similar studies performed for cerebral angiography, we decided against using this as a single primary endpoint as thousands of patients would be required. We opted for a composite primary end point of nausea, vomiting, abdominal pain, emergency intubation and aspiration. These will be recorded both immediately intra/post procedure by the operation physician and again by the patient within 8 hours after the procedure. We will compare the two groups using 95% confidence intervals to ascertain the extent to which they overlap. Secondary end points will be overall patient satisfaction, the incidence of hypoglycaemia and hypotension, and 30 day chest infection rate which will be compared between the two groups.

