7.1 Sample Size Determination

With 200 participants in each group, if none of the participants has an event then the upper limit of the 95% confidence interval for event rate would be 1.5%. Hence if both groups, fasting and non-fasting, have no events recorded then it is highly unlikely that the event rate in the two groups would differ by more than 1.5%. Provided that a difference of 1.5% in event rate is deemed not clinically meaningfully different; then 200 participants in each group would demonstrate that not fasting has a similar event rate to fasting.

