7.3 Interim Analyses

Final Analysis will take place once all data is collected. However, if sequentially the first 10 patients in the non-fasting group show signs of an event rate in excess of that shown in the fasting group as demonstrated by non-overlapping confidence intervals then stopping rules will be applied. For this pilot study, this will be monitored by the Chief Investigator.

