9.3 Records Retention

All records will be archived for 5 years in line with the Trust R&D Policy.

10 Study Monitoring, Auditing, and Inspecting

The investigator will permit study-related monitoring, audits and inspections by the Ethics Committee, the Sponsor and the Research Governance Manager.

Participation as an investigator in this study implies adherence to the principles and responsibilities of the Research Governance Framework, ICH/GCP and Directive 2000/20/EC

11 Ethical Considerations

The patient will receive a detailed description of the study in the patient information sheet send together with pre-procedure assessment letter by mail (around 1 week before the pre-procedure assessment clinic date) to give him/her time to think about the study. Then, at the pre-procedure assessment clinic, they will have the opportunity to ask questions with one of the research team and to answer any queries. Any patient will have the right to abstain from taking part into the study or to withdraw after taking part without affecting the standard of care they are receiving.

The Chief Investigator will ensure that the risk of the study does not outweigh the benefit at any point during the study time, and if so, the study will be prematurely terminated.

The benefit /risk of taking part into the study will be adequately explained to the patients. There will be no direct benefit to the patient from taking part in this study. However, the information gained from the study will help improve the quality of service offered to the patients, increase their satisfaction, may aid in changing the current practice and avoiding unnecessary delay to the patients. The potential risk will be made clear which is the occurrence of nausea and vomiting at an expected rate of 1-2% and no expected emergency endotracheal intubation or aspiration pneumonia cases.

Once patient is enrolled in the study, all his personal information will be anonymized with the only identifier the study number. All patient data will be password protected on the computer in the cath lab. All health professionals involved in the study and patient care will have access to this

information if required. Only the CI will have access to identify the patient personal data for the purpose of safety.

To ensure un-biased result, an adequate randomization process with intention to treat analysis will be undertaken. Analysis will be done by the Sub-Investigator who is blinded to group allocation.

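### Section 7.1 justifies 200 per group only for zero events in both groups, while the protocol itself expects 1–2% nausea and vomiting; similarity within 1.5 points cannot be relied on

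*Combined protocol and SAP*

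**What the plan says.** Section 7.1 is the only justification for 200 patients per group. It says that with no events among 200 the upper 95% confidence limit for the event rate is 1.5%. It continues "if both groups, fasting and non-fasting, have no events recorded then it is highly unlikely that the event rate" would differ between groups by more than that amount. Provided 1.5% is accepted as clinically unimportant, it concludes "then 200 participants in each group would demonstrate that not fasting has a similar event rate to fasting".

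Other sections bear on the zero-event condition:

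- Section 3.3: "Primary endpoint is a composite of nausea, vomiting, abdominal pain, emergency intubation and aspiration".
- Section 11, on the risk to be explained to patients: "the occurrence of nausea and vomiting at an expected rate of 1-2" per cent.
- Section 2.1, from a published study: "incidence of nausea and vomiting was reported to be 1% before elective cerebral angiography", with no significant difference between fasting and non-fasting patients.
- Section 7, on aspiration alone: "we decided against using this as a single primary endpoint as thousands of patients would be required".
- Section 2.2: the first objective is to show that eating before the procedure "is not associated with any increased risk of nausea, vomiting, abdominal pain" and the other components.

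Section 7.2 plans a 95% confidence interval and Fisher's exact test for the composite. It names no interval method and ties neither analysis to the 1.5-point margin. Section 7.3 calls the trial a pilot: "For this pilot study, this will be monitored by the Chief Investigator".

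**The concern.** The sample size argument holds only if nobody in either group has an event, yet the protocol expects events. The composite was chosen because aspiration alone was too rare to study, and section 7.1 then treats the composite as if it too might never occur. Nothing in the plan says what 200 per group would deliver with a few events in each group, which is the case the protocol itself predicts.

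This affects the main safety conclusion. The trial sets out to show no increased risk and to inform guidelines, and section 7.1 is the only support for 400 patients being enough. A reader could combine a non-significant Fisher test with section 7.1 and conclude that the groups had been shown to agree within 1.5 points, when the interval allowed a clearly larger excess in the non-fasting group.

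**Working it through.** **Inputs.** n = 200 per group and a margin of 1.5 points (section 7.1); 1:1 allocation (section 4.3); event rate p of 1% to 2% (section 11, with 1% cited in section 2.1); a 95% interval between groups (section 7.2). Assumptions: p applies to the composite, and the true rate is the same in both groups.

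**1. The plan's own figure.** For 0/200 in one group:
- rule of three: 3/200 = 1.50%
- exact one-sided 95% limit: 1 − 0.05^(1/200) = 1.49%
- exact two-sided 95% limit: 1 − 0.025^(1/200) = 1.83%

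So 1.5% reproduces as a one-sided bound for a single group. It is not labelled as one, and it is not an interval for the difference between groups.

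**2. How likely is the zero-event case?** Expected events per group are 200p, which is 2 at 1% and 4 at 2%. The chance of none in 400 is (1 − p)^400:
- 0.99^400 = 0.018
- 0.98^400 = 0.0003

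**3. Width with equal observed counts.** Newcombe's upper limit is d + √[(u₁ − p₁)² + (p₂ − l₂)²], where d = p₁ − p₂, group 1 is non-fasting, and l and u are the Wilson limits for each group.
- 2 v 2: each rate is 1%, Wilson limits 0.27% to 3.57%; √(2.57² + 0.73²) = 2.67 points.
- 4 v 4: each rate is 2%, Wilson limits 0.78% to 5.03%; √(3.03² + 1.22²) = 3.27 points.

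Wald's half-width, 1.96 × √[2p(1 − p)/200], is 1.95 and 2.74 points. All four exceed 1.5. They are 1.8 and 2.2 times the margin by Newcombe, and 1.3 and 1.8 times by Wald.

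**4. Chance that the upper limit is below 1.5 points.** Exact binomial enumeration over both groups with equal true rates, two-sided 95% limits:

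| True rate | Zero events in 400 | Newcombe | Wald |
|---|---|---|---|
| 0.5% | 13% | 26% | 74% |
| 1% | 1.8% | 22% | 45% |
| 2% | 0.03% | 15% | 23% |
| 3% | 0.0005% | 12% | 16% |

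Wald has zero width at 0 v 0, so it is unreliable at these counts. By two-sided Newcombe, no result with as many or more events in the non-fasting group passes; even 0 v 0 gives 1.88 points. Passing requires fewer events in the non-fasting group, for example 0 v 1 (upper limit 1.43), 1 v 3 (1.48) or 2 v 5 (1.44).

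**5. What the trial can exclude.** The 80th percentile of the Newcombe upper limit is 3.69 points at 1% and 4.60 at 2%. These are the excesses that 200 per group would exclude with 80% probability (80% is an assumption; the plan states no power).

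**6. What the 1.5-point claim would need.** By normal approximation with one-sided 2.5% and 80% power, n per group = (1.960 + 0.842)² × 2p(1 − p)/0.015², which gives 691 at 1% and 1,368 at 2%.

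**The case against.** Five points can be made for the plan.

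*Section 7.1 is conditional and never predicts zero events.* This is true of its first two sentences. The last sentence drops that condition and keeps only the proviso about 1.5%, so the claim about 200 per group stands unqualified.

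*The check is stricter than the plan's own bound, which is one-sided.* This is fair. With a one-sided 95% limit, the chance of falling below 1.5 points rises to 34% and 23% (Newcombe) or about 50% and 30% (Wald) at rates of 1% and 2%. Equal counts then give upper limits of 2.1 points (2 v 2) and 2.6 points (4 v 4) by Newcombe, and 0 v 0 passes at 1.33. The failure at 0 v 0 therefore depends on the two-sided reading. The failure at the expected event counts does not.

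*The 1–2% is a risk stated to patients, not a design rate, and is not split by group.* This is also fair, which is why the table runs from 0.5% to 3%. Only Wald at 0.5% looks favourable, at a rate below the protocol's range and with a method that breaks down there. The rate covers nausea and vomiting only, so the remaining components can only raise the composite. If the non-fasting rate were truly the higher one, excluding an excess would be harder still.

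*The trial is called a pilot.* Sections 7.3, 12, 13 and 14 say so, although section 12 ties its funding statement to the first 50 patients while sections 1 and 3.5 give 400. The label does not cancel the confirmatory wording in sections 2.2 and 7.1.

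*The 1.5% is correct.* It is, for one group with no events.

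**Conclusion.** The concern holds and must be fixed. The zero-event case behind the sample size has a chance of 1.8% or less at the protocol's expected rate. In the likely case of a few events per group, the trial would more often than not fail to exclude a 1.5-point excess on a two-sided 95% interval, by either method. On the one-sided reading most favourable to the plan, the chance of success is at best about even.

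The sizes rest on equal true rates in the two groups, on applying 1–2% to the whole composite, and on the choice of interval method, which the plan leaves open. The conclusion survives reasonable changes to these; the exact percentages do not. The fault lies in carrying a single-group zero-event bound over to a comparison in which events are expected.

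**What to change.** - Rewrite section 7.1 at an event rate of 1–2%, stating that this is assumed for the composite.
- Name one method for the interval on the difference, for example Newcombe's, in sections 7.1 and 7.2, and state its sidedness.
- Withdraw the claim that 200 per group would demonstrate similarity within 1.5%.
- State the precision by the named method. With Newcombe, equal observed rates of 1% to 2% give about ±2.7 to ±3.3 points, and an excess of about 3.7 to 4.6 points can be excluded with 80% probability. If normal-approximation figures are given instead (2.8 × √[2p(1 − p)/200] = 2.8 to 3.9 points, one-sided 2.5%), label them as such.
- Keep the 1.5% figure only as the one-sided bound for a single group with 0/200, and note that the two-sided exact limit is 1.83%.
- If 1.5 points stays as the margin, describe the trial against it as a pilot or estimation study, reword the first objective in section 2.2 to match, and reconcile the pilot wording in section 12 with the 400 patients elsewhere.

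The cost is a rewritten paragraph in 7.1, one line in 7.2 and aligned wording elsewhere. No extra patients or data are needed, but the stated precision becomes less favourable. Keeping the confirmatory claim instead would take about 691 to 1,368 patients per group on the assumptions above.

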7.2 Statistical Methods

Our composite primary endpoint will be analysed using 95% confidence interval between the fasting and non-fasting group and the event rate will be compared using the Fisher's exact test. Categorical secondary outcomes will be presented as number and percentages and compared between the two groups using the Chi-square test or Fisher's exact test. Secondary continuous outcomes will be presented as mean and standard deviation and compared using the independent samples t-test. P-values will be used to assess evidence of difference. Any P value < 0.05 will be considered significant.

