Duration	12 months
Participating Centres	Blackpool Victoria Hospital
Primary End Point	Composite of nausea, vomiting, abdominal pain, emergency endotracheal intubation and aspiration,
Number of participants	400 patients
Main Inclusion /Exclusion Criteria	INCLUSION

	
1. All patients >18 years undergoing elective coronary angiography or angioplasty procedures in the 2 months window.
 
EXCLUSION
 
 1. Patient choice 2. Other cardiac procedures such as EP studies, pacing, structural heart disease intervention 3. Emergency PPCI 4. Patients already admitted in the hospital with UA / NSTEMI 5. Patients unable to give informed consent

Statistical Methodology and Analysis
	
Our composite primary endpoint will be analysed using 95% confidence interval between the fasting and non-fasting group using the Fisher's exact test. Categorical secondary outcomes will be presented as number and percentages and compared between the two groups using the Chi-square test or Fisher's exact test. Secondary continuous outcomes will be presented as mean and standard deviation and compared using the independent samples t-test. P-values will be used to assess evidence of difference. P value <0.05 will be considered significant.

2 Introduction

This document is a research protocol and this study will be conducted in compliance with the protocol, The Research Governance Framework, International Conference on Harmonisation, Good Clinical Practice Guideline ICH/GCP, and all applicable Blackpool Teaching Hospitals NHS Foundation Trust Research Office requirements.

This study aims to demonstrate that pre procedural fasting for elective cardiac procedures is unnecessary and outdated practice. It is without doubt that induction of general anaesthesia depresses cough and swallow reflexes and therefore increases the risk of aspiration with airway manipulation. However, coronary angiography and angioplasty does not require general anaesthesia and is carried out purely under local anaesthetic. So why do we still need periods of fasting?

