4.3 Randomisation Process

Randomisation will take place in pre-procedure assessment clinic in a 1:1 ratio using sealed enveloped method. This information (whether fasting or not) will be relayed to the patient at the time of pre-procedure assessment and also stored on a spreadsheet with study number the only identifying factor. This will be password protected with individuals directly involved having access to this. This data will also be backed up on a password protected computer in the catheter laboratory.

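### Fisher's exact test is valid but very conservative with 200 per arm and rare events, so it gives up sensitivity to harm that a named exact unconditional test would recover at the same sample size

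*Combined protocol and SAP*

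**What the plan says.** Section 7.2 (Statistical Methods) gives the primary analysis two parts. The first is an interval: "Our composite primary endpoint will be analysed using 95% confidence interval between the fasting and non-fasting group". The second is a test: "the event rate will be compared using the Fisher's exact test". The Section 1 summary merges them: "Our composite primary endpoint will be analysed using 95% confidence interval between the fasting and non-fasting group using the Fisher's exact test". No interval method is named. The introduction to Section 7 says the intervals will be used to see how far the two groups overlap.

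On significance, Section 7.2 says "P-values will be used to assess evidence of difference" and "Any P value < 0.05 will be considered significant". Sidedness is not stated. Categorical secondary outcomes may be compared by chi-square or Fisher.

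Section 7.1 fixes the size at 200 per arm and reasons from a result with no events in either arm, treating a 1.5-point difference as not clinically meaningful. The only expected rate for any part of the composite in this trial is in Section 11: "occurrence of nausea and vomiting at an expected rate of 1-2" per cent, with no intubation or aspiration pneumonia expected. Section 2.1 cites 1% for nausea and vomiting from a cerebral angiography study. The composite also contains abdominal pain (Section 3.3), and no rate for the whole composite appears anywhere. The first objective in Section 2.2 is to show that eating freely brings no increased risk.

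**The concern.** Fisher's test conditions on the total number of events. When that total is small, few outcomes are possible and the attainable P-values are far apart, so the real false-positive rate can fall well below the nominal 5%. In an ordinary superiority trial this is caution. Here a finding of no difference is the outcome the investigators hope for, so a test that seldom rejects works in favour of the desired conclusion. At stake is the chance of flagging a real excess of events in the non-fasting arm. The same applies to any rare secondary outcome for which Fisher is chosen.

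**Working it through.** **Inputs.** 200 per arm (Section 7.1); 1:1 allocation (Section 4.3); P<0.05 (Section 7.2); event rates of 1-2% from Section 11, extended to 10% because the composite rate is unknown. Assumed: two-sided test, independent binomial arms, 200 analysed per arm.

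**The plan's own figure.** Section 7.1 gives an upper 95% limit of 1.5% for 0 events in 200. The rule of three gives 3/200 = 1.50%, and the exact one-sided limit is 1 − 0.05^(1/200) = 1.49%, so it reproduces as a one-sided limit. The two-sided Clopper-Pearson limit is 1.83%. The figure does not involve Fisher's test.

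**Single results, by hand.** With 0 fasting and k non-fasting events, the two-sided Fisher P is 2 × C(200,k)/C(400,k):
- k=4: 2 × (200·199·198·197)/(400·399·398·397) = 2 × 0.0616 = 0.123
- k=5: 0.123 × 196/396 = 0.061
- k=6: 0.061 × 195/395 = 0.030

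Fisher therefore needs 6 events against none (3% v 0%). The pooled score statistic is z = (p1 − p2)/√[p̄(1 − p̄)·2/200]. For 0 v 4, z = 0.02/√(0.01 × 0.99 × 0.01) = 2.01. Its exact unconditional P, the largest tail probability over all common event rates, is 0.047; for 0 v 5 it is 0.025. That test needs 4 events (2% v 0%).

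**Actual size.** Size(p) = Σ Bin(a; 200, p)·Bin(b; 200, p) over all tables (a, b) that the test rejects, enumerating all 201 × 201 tables:

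| Common rate | Fisher | Unconditional, pooled score |
|---|---|---|
| 1% | 0.49% | 4.05% |
| 1.5% | 1.18% | 4.56% |
| 2% | 1.72% | 4.28% |
| 3% | 2.2% | 4.1% |
| 5% | 2.9% | 4.6% |
| 10% | 3.4% | 4.4% |

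The largest size over all rates is 4.0% for Fisher and 4.96% for the unconditional test. Every table that Fisher rejects is also rejected by the unconditional test.

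**Power to flag harm** (same sum, arms at different rates, rejections in the harm direction only):

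| Fasting v non-fasting | Fisher | Unconditional, pooled score |
|---|---|---|
| 1% v 2.5% | 9.6% | 18.3% |
| 2% v 3.5% | 8.1% | 12.6% |
| 1% v 4% | 36.0% | 47.0% |
| 2% v 6% | 44.0% | 52.8% |
| 5% v 10% | 40.6% | 46.0% |
| 10% v 20% | 76.8% | 79.8% |

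**The choice of statistic matters.** Boschloo's test is also exact and unconditional, but it uses the Fisher P-value as its statistic. Its size at 1%, 1.5% and 2% is 0.49%, 1.19% and 1.79%, and it still needs 6 events against none. It recovers almost nothing here.

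**The case against.** The strongest reply is that nothing in the plan is wrong. Fisher at P<0.05 holds its level and is a conventional choice for sparse tables. That stands: a reader might infer from a 0.5% size that the stated alpha is wrong, but a level-5% test only promises an error of at most 5%. The issue is lost sensitivity.

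Second, a reader might take 1-2% as the trial's expected primary event rate. The documents do not say so. Section 11 gives it for nausea and vomiting, while the composite adds abdominal pain and is also reported by the patient within 8 hours (Section 7). If the composite is commoner, the gain shrinks to about 5 points at 5% v 10% and 3 points at 10% v 20%. It does not reverse.

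Third, the P-value is not the only primary analysis, and the similarity argument in Section 7.1 rests on an interval limit. With no events in either arm the choice of test changes nothing. This is fair, but the interval method is unnamed, and judging overlap of two separate intervals is itself a conservative comparison, so it does not make up the loss.

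Fourth, it is tempting to think that a better test would make a non-significant result reassuring. It would not: for a 1.5-point harm the unconditional test has only 13-18% power, so it misses such a harm 82-87% of the time. The missing comparison of an interval with a margin is the larger weakness.

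For the secondary outcomes the loss is conditional, since Section 7.2 also allows chi-square.

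**Conclusion.** The point holds as a matter of efficiency in a safety comparison. At rates of 1-2%, Fisher runs at about a tenth to a third of its nominal error (0.49/5 to 1.72/5). A valid test that rejects everything Fisher rejects, and more, is available at the same sample size. The gain in power is about 9-11 points for harms of 3-4 points over a 1-2% baseline, and about 5 points at 5% v 10%. For the 1.5-point difference named in Section 7.1 it is 9.6% to 18.3% from a 1% baseline, and 8.1% to 12.6% from 2%.

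These figures assume a two-sided test, independent binomial arms and 200 analysed per arm, and their size depends on a composite rate that the protocol does not give. The change is worth making but secondary: it improves the chance of noticing harm and does not turn non-significance into evidence of similarity.

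**What to change.** In Sections 1 and 7.2, for the primary composite and for rare categorical secondaries where Fisher would be used, pre-specify the two-sided exact unconditional test with the pooled score statistic. Name the statistic, because an unspecified exact unconditional test could be read as Boschloo's. State that software computes the P-value exactly: a rounded cut-off of z = 2.000 has a maximum size of up to 5.1%. Report the test with a 95% confidence interval for the risk difference by a named method, such as Miettinen-Nurminen, in place of judging overlap of the groups' intervals.

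The cost is a few sentences of analysis wording and no extra patients. There are two downsides. The test is less familiar. The exact P-value and the interval can also disagree at the border: at 3 v 10 events, z = 0.035/√(0.0325 × 0.9675 × 0.01) = 1.97, so the Miettinen-Nurminen interval excludes zero while the exact P is 0.051. The plan should say in advance which governs.

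Separately, any claim of similarity should rest on the upper confidence limit of the risk difference compared with a stated and justified margin.
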